1. To examine feasibility of implementing a simplified physical examination (SPE) aimed at identifying patients suited to cervical spine OMT and neuromuscular/ sensorimotor retraining, within a New Zealand Primary Health Care setting.
2. Based on response to treatment over time, to provide preliminary evidence regarding the

efficacy of the simplified physical examination to accurately identify individuals who may be suited to physiotherapeutic intervention consisting of OMT and neuromuscular/sensorimotor retraining. Included in this objective will be use of data to validate a clinical objective oculomotor screen to improve clinical utility of the SPE.

We hypothesise that using the SPE will aid in identification of individuals suited to orthopedic manual therapy of the neck. Consequently, primary outcomes including clinician attitude toward using the SPE in a primary health care setting, and participant compliance and satisfaction with the OMT intervention will be positive. Further we anticipate that measurable improvement (objectively assessed neck function and clinical presentation) in response to the selection to neck OMT based on the SPE will be observable over time. Results will therefore support feasibility of using the SPE for acute patient assessment, as well as the clinical efficacy of this approach for managing neck related signs and symptoms following concussion.

Methods

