Smooth Pursuit/ Neck Torsion: The patient is seated comfortably with the head positioned in neutral and is asked to follow a slow-moving target approximately 40° (20° to the right and to the left). The patient is instructed to keep the head still while observing the target. This is repeated in neutral and in cervical torsion (rotation of the trunk to the left or right underneath the head, rather than turning the head left or right). Differences in eye motion are noted with differences between neutral and cervical torsion being associated with cervical sensorimotor disturbance, as opposed to vestibulo-ocular impairment which may be more apparent in neutral [54].

Ethical considerations for clinical measures of neck function and head movement control: There is a risk of symptomatic aggravation such as increased dizziness or nausea, or soreness in the neck muscles following assessment based on previous participant reports, however all symptoms have been short-lived and (dizziness usually settles with a short break following test performance). Muscle endurance tests have the potential risk of mild muscle strain or post exercise soreness. However, there is minimal likelihood of injury as testing is performed within the participants tolerance levels. Any muscle discomfort or soreness associated with the endurance test is usually short lived and resolves within 24-48 hours. Participants will also

be offered a short break if required during testing to allow time for symptoms to settle.

Measures of vestibulo-ocular performance: will be used to identify individuals with evidence of vestibulo-ocular impairment [55]. Vestibulo-ocular assessment will commence with oculomotor screen of eye movement to determine presence or absence of baseline oculomotor paresis or palsy [56] which may unduly influence VOS results. This will be followed by completion of the oculomotor and vestibular testing suite (recorded as present/ absent: nystagmus, saccades, strabismus, canalith disorders, vestibulo-ocular reflex function impairment [gain]) on the ICS Chartr 200 VNG System (Otometrics; Taastrup; Denmark). Two or more positive tests will identify individuals with evidence of vestibulo-ocular impairment [57, 58].

Description of the vestibulo-ocular assessment is as follows:

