Participants identified as eligible for entry to treatment arm: will include those participants who demonstrate positive findings for a minimum of 3 cervical spine musculoskeletal and or sensorimotor outcome [12] as well as an absence of 2 or more positive oculomotor indicators of vestibulo-ocular impairment [55, 57]

Participants identified as ineligible for entry to treatment arm: identified due to an absence of sufficient positive neck related physical assessment findings, or alternately a positive

vestibulo-ocular screen will be provided with standardised graduated return to activity information [14, 70] as well as appropriate referral where evidence of vestibulo-ocular or physiological impairment is identified by the SC.

Of note, the SC conducting the laboratory-based screening session will be a New Zealand registered physiotherapist, and hold a current annual practicing certificate, Physiotherapy New Zealand membership, and ACC registration. They will hold additional training in OMT with a minimum of 3 years clinical experience. They will also have received specialised training from the PI (OG) in assessments to be used during the screening session including performance of testing, data reduction, and analysis of quantifiable outcomes necessary to establish participant eligibility for enrolment in the treatment arm of the study.

Estimated duration of total testing time will be 1.25 hour (1 hour for the SPE and 0.25 hours for induction and consent). All participants who provide consent and complete the SPE will be provided with a \$40 voucher to recognise the reasonable costs involved with participating in this study.

Treatment Sessions:

Treatment sessions procedure:

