We will use Thematic Analysis, an evaluative deductive approach to analyse the qualitative focus group and interview data, as described by Clarke and Braun [77]. The SC will code each transcription and one of the researchers will code every third transcription, grouping the codes into themes and sub-themes. An iterative process will be used within the research team to define the main themes and emerging models related to the study aims. In this way thematic analysis will be reflexive to aid in identification of any instances where the PI's beliefs may unduly influence identification of these main themes.

Quantified feasibility outcomes: activity, compliance, and adverse event monitoring

Participants will record daily performance of home exercises prescribed by the treating therapist in an activity-log (yes/ no, minutes of exercise per day) to determine treatment compliance. Non-attendance at scheduled treatment sessions will be recorded by the treating therapist (yes/no per session) as well as any adverse reactions to treatment (number). Participants will complete an exiting questionnaire to assess patient satisfaction [78].

Experimental Outcomes:

Experimental outcome measures (experimental studies a. & b.) will include but are not limited to:

Category	Exploratory OM
Cervical Spine	

Kinematic Assessment - Virtual Reality	Total range of motion (deg) Peak Velocity – Rotation R (deg/s) Peak Velocity – Rotation L (deg/s) Peak Velocity – Rotation Ext. (deg/s) Global head motion accuracy (deg)
Muscle Function (CFET)	Total time (sec)
Manual Spinal Examination	Pos/ neg
Sensorimotor Function (JPE)	Degrees Error (deg) Neck Disability Index (tot/ 50) Headache Impact Test-6
Vestibulo-Ocular	
VNG OM Assessment	Full Assessment (≥ 2 pos/neg overall (pos/neg) ; pos/neg per assessment)
VOMS assessment	Increase in symptoms (11- point NRS) ; avg NPC > 5cm Dizziness Handicap Index
Participant Outcomes	
Physical Activity : Actigraphy	Minutes of Vigorous Physical Activity, min/day Physical Activity (TAC/d; steps/d; PAEE - kcal/kg/day) Activity log Consensus Sleep Diary PROMIS sleep questionnaires IPAQ (METs) Fatigue Severity Scale
Quality of Life	EuroQol-5D-5L (EQ VAS)

Data Management

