Linear mixed method analysis of repeated experimental outcomes will determine treatment effect. Effect modifiers including sex and age as well as statistically significant demographic confounders will be included in the final model. Further secondary analysis may be undertaken using data collected at all time points. Multivariable linear regression will identify items of the VOMS which best predict VNG OM.

Data storage:

All data (including patient and health practitioner data) will be stored on the personal password-protected laptops of the PI ([name]) and or the password-protected study laptop. Any hard copies of the questionnaires and consent forms will be stored in the PI's office in a secure filing cabinet. Only the researchers mentioned in the application and the SC (tba) responsible for processing and analysis will have access to the de-identified data collected during the study. The principal researcher ([name]) and the SC will keep a list identification codes with participant names, so that participants can be identified by their coded data if needed.

A standardised hard copy of the summary report of the participants findings from the screening session completed by the SC will be provided to the treating physiotherapist (via postal mail). This will not be de-identified since it will be used by the treating physiotherapist to inform treatment. A copy of these reports will be kept on the PI's personal password-protected laptop.

The treating physiotherapist will record the clinical assessment and treatments, as required, on their usual practice management systems as well as information related to study feasibility.

All data will be stored for the duration of the study on the primary investigator's password-protected University laptop and will be accessible by members of the research team. It will also be stored for at least 10 years in the school's archive folder on the High-Capacity Storage System (HCSS). Any personal information held about the participants (such as contact details and hard copy questionnaires) may be destroyed at completion of the research. Coded study information may be kept by the University of Otago in secure, cloud-based storage indefinitely. All storage will comply with NZ I data security guidelines.

Potential problems: (medical/legal; issues with disclosure; conflict of interest, etc)

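### Linear models are specified for the pos/neg VNG and manual-examination outcomes, and selection leaves overall VNG no room to improve in treated participants

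*Protocol*

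**What the plan says.** - **Aim.** Study Objectives, objective 2, includes using the data to "validate a clinical objective oculomotor screen to improve clinical utility of the SPE".
- **Model for that aim.** Statistical Analysis, Objective 2: "Multivariable linear regression will identify items of the VOMS which best predict VNG OM". The same paragraph assigns a linear mixed analysis to the repeated experimental outcomes, to determine treatment effect.
- **Scale of the outcome.** The Experimental Outcomes table gives VNG OM as "Full Assessment (≥ 2 pos/neg overall (pos/neg) ; pos/neg per assessment". The section on measures of vestibulo-ocular performance has the components "recorded as present/ absent: nystagmus, saccades, strabismus, canalith disorders" and, fifth, impairment of vestibulo-ocular reflex function. The overall rule there is "Two or more positive tests will identify individuals with evidence of vestibulo-ocular impairment". The manual spinal examination (MSE) is likewise listed as pos/neg.
- **Selection.** Eligibility for Entry to Treatment Arm requires, beside the neck findings, "an absence of 2 or more positive oculomotor indicators of vestibulo-ocular impairment [55, 57".
- **Who is tested, and when.** VNG and VOMS are described as part of the screening session, before treatment eligibility is decided. Under Follow up sessions, only people in the treatment arm are re-examined, 1 week and 3 months after treatment.

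**The concern.** The protocol names a method for a continuous outcome and applies it to outcomes that it defines as yes/no. Two consequences follow.

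First, the only analysis named for the validation aim ranks VOMS items by linear coefficients. A clinician deciding whether VOMS can serve as the oculomotor screen needs to know how many VNG-positive people it finds and how many VNG-negative people it wrongly flags. Coefficients do not say this.

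Second, overall VNG status sits among the outcomes whose change is to be read as treatment effect, yet the entry rule sets it to negative for everyone treated. With a single group and no control, any movement in that variable can only look like worsening.

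**Working it through.** **1. Participant flow (Study power).** 160 screened, 60 eligible. 60 × (1 − 0.50) = 30 start treatment, and 30 × (1 − 0.10) = 27 complete. This reproduces the protocol's 30 and 27. The protocol gives no sample size or precision for the VOMS analysis, so there is no further figure to reproduce.

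**2. Linear model on a 0/1 outcome.** Assumed, because the document does not give them: seven correlated predictors, two truly predictive, and VNG-positive prevalence of 10% to 50%. With n = 160 and 500 simulated data sets per prevalence:

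| Prevalence | Fitted values outside 0–1 | Same top item as logistic | True best item found: linear / logistic |
|---|---|---|---|
| 10% | 21.7% | 92.4% | 73.0% / 74.2% |
| 20% | 16.2% | 93.6% | 82.6% / 82.6% |
| 30% | 12.3% | 97.4% | 86.6% / 86.4% |
| 40% | 9.8% | 98.2% | 84.8% / 85.8% |
| 50% | 8.8% | 98.2% | 85.4% / 85.6% |

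The linear model therefore gives impossible predicted probabilities but ranks items about as well as logistic regression.

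**3. Overall VNG in treated participants.** I read the eligibility indicators as the same tests that define overall VNG. Entry requires 0 or 1 positive and the outcome is positive at 2 or more, so 0 of about 30 are positive at baseline. The possible changes are 0 → 0 or 0 → 1. A baseline regression restricted to this group would have a constant outcome (total sum of squares 0, all coefficients 0).

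**4. Per-test VNG in treated participants.** One positive test is allowed. For K independent tests, each positive with probability q, the share of eligible people with exactly one positive is p1/(p0 + p1), where p0 = (1 − q)^K and p1 = Kq(1 − q)^(K−1). With assumed K = 5, q = 0.05: 0.204/(0.774 + 0.204) = 0.21. With K = 8, q = 0.20: 0.336/(0.168 + 0.336) = 0.67. Per-test results can therefore improve or worsen.

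**5. What the screening visit can deliver.** The half-width for an assumed sensitivity of 80% is 1.96 × √(0.8 × 0.2/n), with n the number of VNG-positive people among 160:

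- prevalence 10%: n = 16, ±0.196
- prevalence 20%: n = 32, ±0.139
- prevalence 40%: n = 64, ±0.098
- prevalence 62.5% (ceiling: all 100 ineligible people VNG-positive): n = 100, ±0.078

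For an assumed specificity of 80%, the 128 and 96 VNG-negative people at 20% and 40% prevalence give ±0.069 and ±0.080.

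At 20% to 40% prevalence the smaller outcome class holds 32 to 64 people. With seven assumed items that is 32/7 = 4.6 to 64/7 = 9.1 per item. The logistic model can be fitted, but it is not richly supported.

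**The case against.** The best defence is that the stated task is to pick out items. Linear coefficients on a 0/1 outcome are risk differences, so they are interpretable, and step 2 shows that they rank items much as logistic regression does. This stands: the planned regression is ill-suited but would not fail outright. It does not rescue the aim, since ranking items is not validating a screen.

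It can also be said that VNG yields quantities, such as reflex gain, and that a count of positive tests could be formed. The protocol lists neither as an outcome; it lists pos/neg only.

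A statistical analysis plan not shown here may fix the analysis set and the accuracy measures. Their absence is therefore not held against the protocol. The point is the named model, which conflicts with the protocol's own outcome table.

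Several stronger readings are tempting and are not supported:

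- *The validation cannot be estimated because treated people are VNG-negative.* Nothing confines it to treated people. VNG-positive people are tested at screening too.
- *Treated people would be counted three times.* The mention of all time points belongs to a separate sentence about further secondary analysis, not to the VOMS regression.
- *VOMS is meant to replace laboratory VNG.* The objective speaks only of better clinical utility.
- *The change analysis would show spurious deterioration.* Assuming five tests, reliability 0.7, inter-test correlation 0.3, per-test positivity of 10% to 30% and no true change, 6% to 22% would turn positive at retest. An assumed recovery of 0.3 SD lowers this to 2% to 9%, and 0.5 SD to about 1% to 4.5%. Participants enter within 14 days of injury, so zero recovery is a strong assumption.

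**Conclusion.** The point holds in a limited form. The linear regression for VNG OM, and the linear mixed model as applied to MSE and VNG, do not fit outcomes that the protocol defines only as pos/neg. This follows from the text without assumptions. The 9% to 22% of out-of-range fitted values rests on the simulated settings.

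Overall VNG in the treated group cannot show improvement. That is also structural, given that eligibility and outcome use the same rule. Per-test VNG is not disabled, although selection caps each person at one positive test at entry.

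Severity is moderate to minor. The protocol makes feasibility primary and labels these outcomes exploratory. Most of the other listed outcomes are measured in degrees, seconds or scores, for which a linear mixed model is a reasonable choice. No data are lost.

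**What to change.** Amend the Objective 2 analysis text:

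1. **VOMS against VNG.** Logistic regression of overall VNG (pos/neg) on the VOMS items, using the screening visit of all screened participants, one record per person. State the VOMS positivity rule or cut-off, and report sensitivity and specificity with confidence intervals.
2. **MSE and per-test VNG over time.** A binary repeated-measures method, for example logistic GEE across visits or exact McNemar tests of each follow-up against baseline. Keep the linear mixed model for the continuous outcomes.
3. **Overall VNG in treated participants.** Report the number of new positives at each follow-up descriptively, and do not present it as a treatment effect.

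Penalised estimation, bootstrap correction and a split at age 40 are optional. A split would thin an already modest number of VNG-positive people.

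The cost is analysis wording only. The VNG and VOMS data are already planned at screening, and no visit, test or participant is added.

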Study Design: This is a mixed methods feasibility study consisting of 3 parts and will investigate clinician and patient response to a ***simplified physical examination (SPE)*** used to inform post-concussion management. Part 1 (Experimental Study a.), a single-group pretest-posttest clinical design will provide preliminary (pilot) evidence of combined effect of assessment and treatment using the SPE to preselect those suited to manual treatment of the neck. Part 2 (Main Feasibility Study) a mixed methods study will consist of a nested qualitative study examining service providers attitudes toward use of the SPE to identify individuals appropriate for neck rehabilitation following concussion (Orthopedic Manual Treatment (OMT) and neuromuscular/ sensorimotor retraining) and utility of this method in the context of current practice. Quantitative exploration of patient compliance, and satisfaction, as well as any adverse reactions to treatment will also contribute to determining overall feasibility of using the SPE. Part 3 (Experimental Study b.), a 3-month follow up will assess long-term effect of treatment selection based on use of the SPE. Combined evidence from these studies will be used to inform development of a future protocol for a pilot randomised, non-inferiority, controlled trial.

Study Procedure and Setting: Participants will take part in one screening session in the Laboratories located at the School of Physiotherapy, University of Otago, Dunedin (referred to as “*screening session*”). Participants identified as eligible to enter the treatment arm of the study will then be invited to participate in further treatment session (referred to as “*treating sessions*”) where they will attend 2 physiotherapy sessions per week for 4 weeks at physiotherapy clinics local to Dunedin. Follow-up assessment (referred to as “*follow up sessions*”) for participants entering the treatment arm of the study will then be conducted 1 week and 3 months following cessation of treatment and will take place at the University of

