The study will be led by the PI, directly supported by the SC. Regular team meetings (face-to-face where possible) will be held to monitor study progress and address any issues arising including those related to potential problems (below), although risk of these is considered very low.

Screening and Follow up Sessions: Participants may feel uncomfortable with the laboratory environment; thus, care will be taken with familiarising them with the researchers, the set up and methods of the study. Participants may be uncomfortable with male or female researchers. To mitigate potential for participants to feel uncomfortable in the research environment they will be informed they are welcome to bring a support person to the laboratory. Other potential problems related to specific outcome measures have been described previously.

Participants will also be informed that in the unlikely event any symptoms resulting from attending the screening session, any of the treatment sessions or the follow up sessions does not subside, or they are concerned that the pain may re-appear, they will be welcome to contact the primary investigator ([name]). If any unresolved concern persist, referral to a GP or physiotherapist of their choice will be considered. If there is lingering pain or symptom reproduction as a result of the study, they will be informed that they may be able to seek an ACC claim to cover treatment of the pain.

Adverse event management: The risk of any adverse event is minimal. In case a participant presents with an adverse event, report to the internal Health & Safety Committee (Centre for Health, Activity and Rehabilitation Research—University of Otago) will be made immediately by the PI (OG) to assess whether reporting the adverse event to the study sponsor, and the Ethics Committee is necessary. If more than one serious adverse event of any kind occurs and if these are related or caused by the treatment interventions, we will suspend the study. If the cause of the events cannot be determined or remediated, and is plausibly related to the intervention, the study will be terminated.

Funding:

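### The mandatory suspension rule counts only serious adverse events tied to the treatment, so serious events caused by the SPE trigger no automatic suspension

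*Protocol*

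**What the plan says.** The study-level rule stands in the Protocol under Adverse event management. Suspension is mandatory on two joint conditions: "If more than one serious adverse event of any kind occurs and if these are related or caused by the treatment interventions". Termination follows in the next sentence: "If the cause of the events cannot be determined or remediated, and is plausibly related to the intervention, the study will be terminated".

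The same paragraph has a wider reporting duty. For any adverse event, whatever its cause, the principal investigator must immediately "report to the internal Health & Safety Committee", so that it can be judged whether the sponsor and the Ethics Committee need to be told.

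Just before this, under Screening and Follow up Sessions, participants are given a contact and referral route in case "any symptoms resulting from attending the screening session, any of the treatment sessions or the follow up sessions does not subside". The opening of Potential problems adds that "Regular team meetings (face-to-face where possible) will be held to monitor study progress and address any issues arising".

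**The concern.** The two conditions in the suspension sentence do different work. The first is open as to the type of event. The second restricts the cause to treatment. A serious event caused by the examination meets the first and fails the second.

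The feasibility of using the SPE is Objective 1, and more people will have it than will have the treatment. It is also a hands-on procedure in recently concussed people. It includes manual pressure over each cervical facet joint with pain provocation recorded, a neck flexor endurance hold, head movement by the assessor, and the Dix-Hallpike manoeuvre. The Protocol puts a red-flag and vascular safety screen in front of the cervical tests, so it treats serious neck pathology at that session as unlikely but possible.

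What is at stake is participant safety. The plan already accepts that more than one related serious event justifies a compulsory pause, and it gives no reason for confining that to treatment.

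**Working it through.** **Step 1: does the term in the suspension rule include the SPE?**

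- Protocol, Interventions: this section describes manual therapy, neuromuscular and sensorimotor retraining, advice and a graded exercise programme. The SPE is not among them.
- Protocol, Study Objectives (hypothesis): the outcomes include "participant compliance and satisfaction with the OMT intervention", which again uses the word for the treatment.
- Protocol, Screening and Follow up Sessions: screening, treatment and follow-up sessions are named one by one when persisting symptoms are discussed. The suspension sentence, a paragraph later, names only the treatment.
- Protocol, Study Design: Part 1 is to give evidence on the "combined effect of assessment and treatment using the SPE". This describes what the pilot evaluates. It does not define the treatment interventions.

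The natural reading of the suspension sentence therefore leaves the SPE out. The termination sentence speaks only of the intervention, without the qualifier. The first two places favour the narrow meaning there too, but Study Design leaves room for the wider one, so that sentence is ambiguous.

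**Step 2: who lies outside the suspension rule?**

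Inputs: 160 planned for SPE screening (Recruitment; Study power); 60 expected to be eligible, 50% declining, 10% dropping out, 30 starting treatment and 27 with complete data (Study power); SPE repeated at both follow-ups (Follow up sessions).

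The plan's own figures reproduce:

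- Start treatment: 60 × (1 − 0.50) = 30.
- Complete: 30 × (1 − 0.10) = 27.

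Participants who have the SPE but never start treatment:

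- 160 − 30 = 130, and 130 / 160 = 81.25%, or 81%.
- Cross-check: (160 − 60) = 100 not eligible, plus 60 × 0.50 = 30 who decline, gives 130.

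No event in these 130 can be caused by a treatment they never receive, so none can count. The 30 who start treatment can contribute treatment-related events. Events caused by their own screening SPE, or by the 2 × 27 = 54 to 2 × 30 = 60 SPEs at follow-up, would not count.

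**Step 3: does another provision require a study-level pause after SPE events?**

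- Red-flag screen (Simplified Physical Examination): stops the assessment of that one person and leads to medical referral.
- Committee report (Adverse event management): covers all events, but its stated purpose is to decide on onward reporting.
- Team meetings (Potential problems): address issues, with no trigger and no required action.
- Contact and referral route (Screening and Follow up Sessions): care for the individual.

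Each reaches SPE events. None obliges the study to pause.

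**The case against.** The strongest reply is that this is a choice, not a mistake. A compulsory count is attached to the repeated therapy, and screening events are left to reporting and judgement. No other section requires the rule to cover assessments. The layers in step 3 also mean that a first serious SPE event would go to a committee at once, before any count was reached. The harms the Protocol expects from the SPE are short-lived dizziness, nausea, soreness or mild strain. Endurance testing stays within tolerance, and the head and neck are supported in the Dix-Hallpike manoeuvre. All of this stands, and it limits the importance of the point. It does not turn a discretionary pause into a mandatory one.

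Three stronger readings are tempting and are not supported:

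- A reader might infer that SPE-related events can never end the study. The termination sentence is unclear on this and is not a plain exclusion.
- A reader might infer that SPE harms go unmonitored. They do not: the duty to report has no limit by cause.
- A reader might try to express the gap as a share of all study sessions or as a probability of two serious events. A session count would treat an examination and a therapy session as equally risky. The number of treatment sessions actually attended is not fixed, because the Protocol allows for missed ones. No serious-event rate is given. Neither figure should be quoted.

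The reply also raises a fair cost. Participants enter within 14 days of concussion, and some could deteriorate after screening for reasons unrelated to it.

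**Conclusion.** The point holds for the suspension sentence. Followed as written, more than one serious event caused by the SPE would force no suspension, and a pause would be left to discretion. The size is one of coverage: 130 of 160 planned participants (81%) fall wholly outside the rule, and the treated participants' own SPEs fall outside it too. For termination the finding is only that the wording is ambiguous.

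This rests on the planned recruitment figures being met and on treatment interventions keeping the meaning used under Interventions. It assumes no event rate, and serious SPE events are expected to be rare. The change is worth making for participant safety. It affects no estimate, analysis or sample size.

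**What to change.** In the suspension sentence, replace *the treatment interventions* with *study procedures (SPE or treatment)* and keep the threshold of more than one serious event. In the termination sentence, use the same phrase in place of *the intervention*, which removes the ambiguity. The order of suspension first and termination second stays as it is.

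The cost is one phrase in each of two sentences, in a single amendment. The practical downside is that serious events after the SPE could then pause or stop the study. Some of these would be hard to attribute, because an effect of the examination can look like natural deterioration in a recently concussed person. That matters most for termination, which also applies when the cause cannot be determined but a link is plausible.
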